- Prospective real-time organoids correlation will be recommended for all the participants if feasible.

Figure 3. Treatment and biospecimen Schema

Tumor Response Assessments

Cross-sectional imaging will be obtained at baseline (within 28 days of treatment commencement) and following initiation of maintenance treatment every 9 weeks (+/- 7 days) until Cycle 10; thereafter imaging will be performed every 12 weeks. If a participant has remained on study for greater than 2 years, imaging can be transitioned to every 3-6 months per MD discretion. Permitted imaging includes: CT chest/abdomen/pelvis with IV and oral contrast or MRI abdomen/pelvis and non-contrast CT chest if patient cannot receive CT IV contrast.

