6.0 CRITERIA FOR PARTICIPANT ELIGIBILITY

6.1 Participant Inclusion Criteria

This is an on-platinum maintenance trial either in a first-line or second-line setting.
 Participants must have either stable disease or responding disease on current first-line or second-line platinum treatment for metastatic disease.

0

POLAR: a phase 2 trial for pembrolizumab and olaparib maintenance for metastatic PDAC and HRD and/or Exceptional Response to Platinum – Ver. 5/3/2020

2. Male or female patients with cytologically or histologically confirmed metastatic pancreas adenocarcinoma or acinar cell carcinoma with homologous recombination gene alterations or platinum sensitivity as per following cohort inclusion criteria below.

Patients will be assigned to cohorts based on their genetic alterations and clinical response. Patient stratification to different Cohorts will be in the order of more canonical homologous recombination-gene (HR-gene) order. For example, patients who meet criteria for both A and B Cohorts, they will be assigned to Cohort A, not B. Cohorts will be defined as following by CLIA-approved NGS or MSK-IMPACT Part A or C:

- Cohort A: Patients with either pathogenic germline or somatic alterations of 3 core HR-genes
 (BRCA1/2, or PALB2) who have stable or responding disease on first-line or second-line platinum therapy in two consecutive imaging assessments over at least 4 months or 16 weeks are eligible for inclusion in Cohort A.
- Cohort B: Patients with either pathogenic somatic or germline non-core 15 HR-gene alterations (ATM, BAP1, BARD1, BLM, BRIP1, CHEK2, FAM175A, FANCA, FANCC, MUTYH, NBN, RAD50, RAD51, RAD51C, RTEL1) who have stable or responding disease on first-line or second-line platinum therapy in two consecutive imaging assessments over at least 4 months are eligible for inclusion in Cohort B.
- Cohort C: Patients without any of the above HR-gene alterations included in Cohort A and B who have platinum-sensitivity, which is defined as a partial response (PR) or complete response (CR) for the best overall response (BOR) during at least 6 months on platinumbased therapy. Variants of unknown significance of candidate HR-genes from Cohort A or B will be eligible for Cohort C if they meet the partial response to platinum criterion.

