- c. Has a known history of active TB (Bacillus tuberculosis).
- 11. Any prior treatment with any PARP inhibitor, including olaparib.
- Any previous treatment with any anti-PD-1, anti-PD-L1, or anti-PD-L2 agent.
- 13. Has received systemic therapy 2 weeks prior to starting treatment
- 14. Patients with any recent investigational agents are not eligible unless at least 2 weeks or 5 half-lives of investigational agent prior to the first dose of study treatment have passed.
- 15. Live vaccines within 30 days prior to the first dose of study treatment and while participating in the study are not permitted. Examples of live vaccines include, but are not limited to, the following: measles, mumps, rubella, varicella/zoster, yellow fever, rabies, BCG, and typhoid vaccine. Seasonal influenza vaccines for injection are generally killed virus vaccines and are allowed; however, intranasal influenza vaccines (e.g., FluMist®) are live attenuated vaccines and are not allowed.
- 16. Active autoimmune disease that has required systemic treatment in the past 2 years is not permitted (i.e. with use of disease modifying agents, corticosteroids or immunosuppressive drugs). Replacement therapy (e.g., thyroxine, insulin, or physiologic corticosteroid replacement therapy for adrenal or pituitary insufficiency, etc.) is not considered a form of systemic treatment.
- 17. Palliative radiotherapy must have been completed 14 or more days before Cycle 1 Day 1.

- 18. If participant received major surgery within 4 weeks before screening, they must have recovered adequately from the toxicity and/or complications from the intervention prior to starting study treatment.
- 19. Participants must have recovered from all AEs due to previous therapies to ≤Grade 1 or baseline. Participants with ≤Grade 2 neuropathy may be eligible. Participants with ≤Grade 2 alopecia may be eligible as well.
- 20. Concomitant use of known strong CYP3A inhibitors (e.g. itraconazole, telithromycin, clarithromycin, protease inhibitors boosted with ritonavir or cobicistat, indinavir, saquinavir, nelfinavir, boceprevir, telaprevir) or moderate CYP3A inhibitors (e.g. ciprofloxacin, erythromycin, diltiazem, fluconazole, verapamil). The required washout period prior to starting is 2 weeks.

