9.0 PRE-TREATMENT/INTERVENTION

 Prior to treatment initiation, all subjects will undergo the following procedures: Separate cross-sectional imaging: CT chest/abdomen/pelvis with contrast or MRI abdomen/pelvis and chest CT without contrast (if IV contrast is contraindicated) within 4 weeks of planned first date of POLAR treatment. Separate CT scans of the chest, abdomen, and pelvis are acceptable, provided they are done 4 weeks of the first treatment.

Research Blood Draws

All collected blood samples at MSK will be processed by the following protocol:

In addition, the following evaluations will be required at the times indicated in Section 11.1 Adverse Event (AE) Monitoring Table 10.

Table 1. Standard-of-care and research blood draws

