13.0 CRITERIA FOR OUTCOME ASSESSMENT AND ENDPOINT EVALUABILITY

13.1. Tumor Measurements

Response Evaluation Criteria in Solid Tumors (RECIST) version 1.1 will be used to determine treatment response. Baseline tumor measurements will be performed prior to initiation of therapy. These measurements should be done according to iRECIST (see Appendix 2) ⁵⁴. An estimate of overall objective and subjective response will be made and recorded at the end of treatment at 8 weeks after the last infusion. Since it is expected that immune activity would lead to tumor flare, the restaging CT scans may be repeated 8 weeks later based on irRECIST and the designation of iCR, iPR, iSD, iUPD, or iCPD will be made at that time. Best overall response will be used.

- **13.1.2.** Disease control rate (DCR): DCR is defined as the percentage of patients who have achieved complete response, partial response, and stable disease to the study treatment.
- **13.1.3.** Overall response rate (ORR): ORR is defined as the percentage of patients who have achieved complete response and partial response to the study treatment.
- **13.1.4. Best Overall Response (BOR):** BOR is defined as the best response recorded from the start of the study treatment until the disease progression/recurrence.
- **13.1.5.** Durable response rate (DRR): DRR is defined as the percentage of patients who had achieved continued disease responses (CR and PR) for more than 6 months.
- **13.1.6.** Durable disease control rate (DDCR): DDCR is defined as the percentage of patients who had achieved continued disease controls (CR, PR, and SD) for more than 6 months from the time from the initiation of study treatment.
- **13.1.7. Additional Assessments.** All patients will have a baseline tumor marker assessment and testing of tumor markers at the designated follow-up time points. Changes in serial tumor marker measurements, in those patients who have baseline elevations, will be utilized as a surrogate marker of clinical response, stable disease or disease progression and reported as such.
- **13.1.8. Patients without residual disease:** For patients whose primary tumor or metastatic disease has been removed or successfully treated, respectively, prior to entry into this trial, progression free survival will be evaluated based on duration of relapse-free survival.
- **13.1.9. Progression free survival (PFS):** PFS is defined as the time from the initiation of study treatment to radiographic progression or death.

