A two stage design will be employed only in Cohort A with co-primary endpoints ORR by iRECIST and 6-month PFS rate⁷ by RECIST v1.1. An initial cohort of 20 patients will be treated. If 14 or more patients are alive and progression free at the 6 months follow-up or if 6 or more objective responses are observed, an additional 13 patients will be accrued for a total of 33 patients. If 23 or more of the 33 patients are alive and progression free at 6 months from start of treatment or if 12 or more objective responses are observed, we can conclude that the regimen is sufficiently active to warrant further testing in this group of patients. We will also evaluate the progression-free survival from the consent date secondarily to the treatment start date (C1D1). We used the reference from historical data for these co-primary endpoints. 6-months PFS rate was 50% and ORR was 20% in singleagent olaparib study arm compared to placebo control arm in maintenance setting⁷. This design yields 81% power to detect a true 6-month PFS rate of 77% or more and it yields 81% power to detect a true ORR of at least 43%. It yields approximately 0.95 probability of a negative result if the true 6-month PFS rate is no more than 53% and the true ORR is no more than 20%. The type I error for the ORR endpoint is 0.02 and the type I error for the PFS endpoint is 0.028 and so the overall type I error of the composite design is bounded at 0.05 (the sum of the two type I error rates for PFS and RR) while the type II error rate for the composite design is 0.09 (each design has a type II error rate of 0.09). The probability of early termination was calculated as the product of the probability of early termination for the PFS endpoint (0.904) and the probability of early termination for the RR endpoint (0.804), resulting in a probability of early termination of 0.73 for the composite endpoint. These calculations assume that ORR and PFS are independent, , the type 1 error slightly decreases if ORR and PFS are positively correlated, which is very likely. The calculations also assume that the 6 month PFS endpoint is binary. Patients who are lost to follow up before their 6 months PFS

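### The response baseline scan need not follow the last platinum dose, so shrinkage from platinum given after that scan can be counted as objective response to POLAR

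*Protocol*

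**What the plan says.** **Scan window.** Protocol Section 4.1 (Tumor Response Assessments) says: "Cross-sectional imaging will be obtained at baseline (within 28 days of treatment commencement". Section 9.0 repeats the limit as "within 4 weeks of planned first date of POLAR treatment", and the screening window in Table 9 is also 28 days. Section 13.1 adds one ordering rule: "Baseline tumor measurements will be performed prior to initiation of therapy".

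**Prior therapy.** Section 6.1, item 1 describes patients still on platinum: "Participants must have either stable disease or responding disease on current first-line or second-line platinum treatment for metastatic disease". The washout for standard systemic therapy is exclusion 13 in Section 6.2: "Has received systemic therapy 2 weeks prior to starting treatment". I read this as no systemic therapy in the 14 days before the first POLAR dose.

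**Use of the scan.** Section 13.1 credits response to POLAR: "ORR is defined as the percentage of patients who have achieved complete response and partial response to the study treatment". Section 14.0 makes ORR decisive in one cohort: "A two stage design will be employed only in Cohort A with co-primary endpoints ORR by iRECIST and 6-month PFS rate". In Cohort A, 6 responses among the first 20 patients are enough to open stage 2, and 12 among 33 are enough to call the regimen active, whatever the PFS result. ORR is also the activity measure for the exploratory Cohorts B and C (Section 2.0).

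**The concern.** Both windows are counted back from the start of POLAR, and neither is tied to the other. The scan can therefore precede the last platinum dose. The first on-study scan, at about week 9, would then be compared with a scan taken while platinum was still being given, and any shrinkage in between would be attributed to POLAR.

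The definition of best overall response does not prevent this: "BOR is defined as the best response recorded from the start of the study treatment until the disease progression/recurrence". It limits when a response may be recorded, but not which treatment produced the change from baseline.

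Carry-over of this kind adds responses, and a single-arm trial has no comparison group in which it would show. The Cohort A ORR rule tests against a fixed null of 20% with a stated type I error of 0.02, so a small upward shift in apparent ORR raises the chance of a false positive noticeably.

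**Working it through.** **1. The window.** Earliest scan: day -28 (Sections 4.1 and 9.0). Latest platinum: about day -14 (exclusion 13). Gap: 28 - 14 = 14 days in which platinum may follow the scan. I looked for a rule that closes this gap in Sections 4.1, 9.0, 13.1 and 13.2 and in the Table 9 imaging footnote. None orders the scan after the last dose, asks for a repeat scan if platinum follows it, or removes such patients from ORR.

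**2. The plan's own figures.** Inputs from Section 14.0: 20 patients, continue at 6 or more responses; 33 patients, success at 12 or more; null ORR 20%; target ORR 43%. The probability that the ORR rule succeeds at response rate p is

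P(p) = Σ (x = 6 to 20) Bin(x; 20, p) × Pr[Bin(13, p) ≥ 12 - x].

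- P(0.20) = 0.0201 (protocol: 0.02)
- P(0.43) = 0.809 (protocol: 81%)
- Stage 1 stop on ORR at p = 0.20: 0.804 (protocol: 0.804)

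The composite type I error is found by enumerating both endpoints. The trial continues if either stage 1 bound is met and succeeds if either final bound is met, with ORR and PFS independent as the protocol assumes. At ORR 20% and 6-month PFS 53% it is 0.0496 (protocol: bounded at 0.05). The model therefore matches the design.

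**3. Effect of carry-over.** The protocol gives neither quantity needed, so both are assumed:

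- f, the share of patients who receive platinum after their baseline scan;
- c, the extra probability in those patients of a response caused by that platinum.

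If the true ORR on POLAR is the null 20%, the apparent ORR is 0.20 + f × c. The 6-month PFS rate is held at 53%.

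| f | c | apparent ORR | extra responses in 33 | ORR type I error | composite |
|---|---|---|---|---|---|
| 0 | – | 20.0% | 0 | 0.020 | 0.050 |
| 10% | 5% | 20.5% | 33 × 0.005 = 0.17 | 0.024 | 0.054 |
| 25% | 5% | 21.25% | 33 × 0.0125 = 0.41 | 0.031 | 0.061 |
| 25% | 10% | 22.5% | 33 × 0.025 = 0.83 | 0.047 | 0.076 |
| 50% | 10% | 25.0% | 33 × 0.05 = 1.65 | 0.093 | 0.122 |

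An average of less than one platinum-driven response in 33 patients (fourth row) more than doubles the 0.020. The composite starts at 0.0496, so it passes 0.05 in every row with carry-over.

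**The case against.** The best case against this point is that the protocol permits the sequence but does not show that it happens or matters. Several parts of that case stand.

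- **Few patients may be affected.** Only those scanned before their last dose can contribute. Adding a shift to all 33 patients without that qualification would overstate the effect.
- **c is probably small.** Cohort A patients have had stable or responding disease over at least 4 months of platinum. A platinum-driven response would need a further response-level decrease from at most 14 more days of treatment. Patients with non-measurable or no evident disease are eligible (Section 6.1, item 6). They are unlikely to contribute a partial response but stay in the denominator.
- **The null may already contain the effect.** The 20% comes from the olaparib arm of a maintenance trial after platinum. If that trial used similar windows, adding carry-over on top counts part of it twice. The protocol does not say.
- **The same window can work the other way.** If platinum stops near a day -28 scan, up to four weeks without treatment follow, and regrowth in that time makes POLAR look worse.

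These arguments limit the size. They do not close the gap: an affected patient's response is still credited to POLAR, and the protocol has no rule by which to recognise it.

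A reader might infer that platinum shrinkage *is* being counted, or that the false-positive rate is badly inflated. The document supports neither. A 10-point lift would give an ORR type I error of 0.253, but it needs, for example, half of all patients affected with c = 20% (0.5 × 0.2 = 0.10). Nor does Cohort C's selection on platinum response bear on these figures, because Cohorts B and C have no pass rule.

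**Conclusion.** The point holds as a gap in the scan rule. The protocol allows the response baseline to precede the last platinum dose by up to 14 days, so shrinkage from that platinum can enter an uncontrolled co-primary endpoint. The window arithmetic is certain. The size of the bias is not: it rests on the assumed f and c, on a true null ORR of 20%, and on a null rate that does not already include the same carry-over. Over the range shown, the ORR type I error runs from 0.024 to 0.093 against the stated 0.02, and the lower part of that range is plausible. No figure in the protocol is wrong here and no two statements conflict. This is a cheap improvement to the scan rule, not a flaw that invalidates the design.

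**What to change.** In Sections 4.1 and 9.0 and in the Table 9 imaging footnote, keep the 28-day limit and add: *the baseline scan used for response is to be obtained after the last dose of prior systemic therapy.* The existing 2-week washout leaves room for this, and neither the washout nor the treatment plan changes.

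For patients already enrolled, flag those whose baseline scan predates the last dose of prior therapy, and report ORR with and without them. This needs only the scan date and the date of the last prior dose.

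Cost: a few patients would need the scan later in screening, or a repeat scan if further platinum is given after it. The rule does not remove carry-over entirely. A scan on the day after the last dose would comply although that dose may not yet have had its effect, so the stated operating characteristics cannot be claimed as fully restored.

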4.0 OVERVIEW OF STUDY DESIGN/INTERVENTION

4.1 Design

This is a phase 2 open-label, non-randomized 3-cohort study to evaluate the safety and clinical efficacy of a novel combination - pembrolizumab and olaparib (POLAR) in genomically enriched three cohorts of metastatic PDAC patients with homologous recombination deficiency (HRD) as below.

Patients will be assigned to cohorts. Cohorts will be defined as following by CLIA-approved NGS or MSK-IMPACT Part A or C:

- **Cohort A**: Patients with either pathogenic germline or somatic alterations of 3 core homologous recombination-genes (HR-genes) (*BRCA1/2*, or *PALB2*) who have stable or responding disease on first-line or second-line platinum therapy in two consecutive imaging assessments over at least 4 months or 16 weeks are eligible for inclusion in Cohort A.
- Cohort B: Patients with either pathogenic somatic or germline non-core 15 HR-gene alterations (ATM, BAP1, BARD1, BLM, BRIP1, CHEK2, FAM175A, FANCA, FANCC, MUTYH, NBN, RAD50, RAD51, RAD51C, RTEL1) who have stable or responding disease on first-line or second-line platinum therapy in two consecutive imaging assessments over at least 4 months are eligible for inclusion in Cohort B.
- Cohort C: Patients without any of the above HR-gene alterations included in Cohort A and B who have platinum-sensitivity, which is defined as a partial response (PR) or complete response (CR) for the best overall response (BOR) during at least 6 months on platinum-based therapy. Variants of unknown significance of candidate HR-genes from Cohort A or B will be eligible for Cohort C if they meet the partial response to platinum criterion.

All the participating patients will receive the combination of pembrolizumab 200 mg IV every 3 week and olaparib 300 mg twice day orally daily continuously (POLAR) as a maintenance therapy. After the first 6 months (9 cycles), on C10D1 Pembrolizumab 400 mg IV every 6 week plus olaparib 300 mg twice a day orally will be continued. Per treating investigator's discretion, patients may remain at Pembrolizumab 200 mg IV every 3 weeks after the first 9 cycles. Additionally, to accomodate patients traveling far distances, if, per treating investigator, after the first or second imaging, there are no toxicities, patient's dosing of Pembrolizumab may change to 400 mg IV every 6 weeks. All cycles will be 21-days (3 weeks) in length.

[figure not shown]

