10.0 TREATMENT/INTERVENTION PLAN

10.1 Administration

Within 4 weeks of screening date, eligible patients will receive combination pembrolizumab and olaparib as maintenance therapy until clinical or radiographic progression or discontinuation due to -limiting toxicity. If a patient requires discontinuation of either olaparib or pembrolizumab for reasons of toxicity and if in the opinion of the treating MD the patient is continuing to derive benefit, the patient is able to continue on study. Additionally, in the absence of unacceptable toxicity, participants who meet criteria for disease progression per RECIST 1.1 while receiving treatment will be permitted to continue treatment, if in the opinion of the treating MD the patient is continuing to derive benefit from the treatment. iRECIST will be used to evaluate the objective response rate and the co-primary endpoint of overall response rate will be assessed by RECIST v1.1. (Section 12.0 CRITERIA FOR REMOVAL FROM STUDY).

The POLAR treatment will be administered to subjects as outlined in Figure 1 - Schematic treatment and biospecimen collection schedule. Approximately within 4 weeks of screen visit, patient will get baseline biopsy and will start the first dose pembrolizumab 200 mg IV every 3 weeks and olaparib 300 mg twice daily orally. After the first 6 months (9 cycles), on C10D1 Pembrolizumab 400 mg IV every 6 week plus olaparib 300 mg twice a day orally will be continued. Per treating investigator's discretion, patients may remain at Pembrolizumab 200 mg IV every 3 weeks after the first 9 cycles. Additionally, to accomodate patients traveling far distances, if, per treating investigator, after the first or second imaging, there are no toxicities, patient's dosing of Pembrolizumab may change to 400 mg IV every 6 weeks. All cycles will be 21 days (3 weeks) in length. Subjects will be monitored for toxicity every three weeks for the first 9 cycles, and every six weeks thereafter, unless clinically indicated to be monitored every 3 weeks.

Table 2. Trial treatment (POLAR)

Drug	Dose	Dose Frequency	Route of Administration	Treatment Period	Use
Pembrolizumab	200 mg	Q3W	IV infusion	Day 1 of each 3- week cycle for cycle 1-9	experimental
Pembrolizumab	400mg	Q6W	IV infusion	Day 1 of every even cycle beginning with Cycle 10	experimental
Olaparib	300 mg (two 150 mg)	BID	Orally	Daily continuously	experimental

The following parameters must be acceptable prior to initiation of protocol treatment:

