- * Computed Tomography (CT) Chest/abdomen/pelvis with oral and IV contrast or CT chest without contrast AND Magnetic Resonance Imaging (MRI) abdomen/pelvis with contrast if IV contrast/iodine allergy. Imaging frequency every 9-weeks from treatment initiation until Cycle 10, then every 12-week thereafter. If a participant has remained on study for greater than 2 years, imaging can be transitioned to every 3-6 months per MD discretion. Imaging evaluation must be done within +/- 7 days of the planned schedule. Per the treating MD's discretion, imaging can be done before the ontreatment biopsy.
- ** Pembrolizumab 400 mg every 6 weeks will be started on Cycle 10 Day 1. Patients will need to come to clinic during odd cycles post Cycle 10, only if clinically indicated. Per treating investigator's discretion, patients may remain at Pembrolizumab 200 mg IV every 3 weeks after the first 9 cycles. Additionally, to accommodate patients traveling far distances, if, per treating investigator, after the first or second imaging, there are no toxicities, patient's dosing of Pembrolizumab may change to 400 mg IV every 6 weeks. Telehealth visits are allowed.
- 1. **Pre-treatment (baseline) Tumor Tissue:** All patients must submit FFPE tumor tissue (#1 core), fresh tissue (75% of #2 core, #3, and #4 core for scRNAseq and only 25% of #2 core for organoid), and flash frozen tumor tissue (#5, 6, and any extra cores for snRNAseq, whole genome sequencing, and MIBI if possible) as per detailed biomarker management plan (BMP). The goal is to obtain 4-6 cores where clinically safe and feasible at baseline within 2-3 weeks before starting the treatment. In patients participating with major PR or CR may not have enough disease at baseline for multiple biopsies.
- 2. **Tumor Biopsy during Treatment (on-treatment) Period:** Repeat biopsy for on-treatment tumor tissue is requested for study purpose for patients between the 6th to 9th week (+/- 1 week) before the first repeat imaging in the 9th week. Per the treating MD's discretion, imaging can be done before the on-treatment biopsy.
- 3. **Tumor Biopsy at End of Treatment (on progression):** Every effort should be made to obtain EOT (+/- 28 days) biopsies in cases of RECIST v1.1 confirmed disease progression if a patient discontinues study treatment due to disease progression, except in instances where the procedure, as performed in the clinical research setting, poses an unacceptable risk to the patient.

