evaluation and who did not respond or do not have documented response before their being lost to follow up will be counted as events (nonresponders/progressors) for the composite primary endpoint. However this will be uncommon. If after the first stage we meet the rule of observing 6 or more responses out of the 20 patients enrolled in the first stage, then no waiting is required and we can proceed with enrollment to the second stage. However, if we do not observe 6 out of 20 responses after the first stage, we will halt accrual after the first 20 patients until we obtain the 6-month PFS status for these 20 patients. The interim look for Cohort A will not affect accrual to Cohorts B and C.

Cohorts B and C will be exploratory and will enroll 15 patients each. ORR will be estimated using the binomial distribution along with exact 95% confidence intervals. With 15 accrued patients, we can estimate the DCR to within +/- 25% margins of error with 95% confidence.

Secondary objectives

Adverse events will be summarized descriptively and tabulated separately for each cohort. DCR will be estimated using binomial proportions along with exact 95% confidence intervals while PFS and OS will be estimated using the Kaplan-Meier method separately for each of the 3 cohorts. CEA and CA 19-9 will be summarized using medians and interquartile range.

Exploratory objectives

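### The Cohort A rule does not name the scan that decides 6-month PFS (the nearest is at week 27, just past the mark), and its loss rule lets lost responders escape the PFS failure count

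*Protocol*

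**What the plan says.** **Decision rule (section 14.0).** In Cohort A, 20 patients are treated first. The PFS part of the rule needs at least 14 of 20 to go on, and the final criterion reads "If 23 or more of the 33 patients are alive and progression free at 6 months from start of treatment". The endpoint is treated as binary. The section states a PFS type I error of 0.028, 81% power at a true rate of 77%, and a 0.904 probability of early termination for the PFS part. The error rate refers to a 53% null.

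**Scan schedule (section 4.1, Tumor Response Assessments).** Imaging is done "following initiation of maintenance treatment every 9 weeks (+/- 7 days) until Cycle 10; thereafter imaging will be performed every 12 weeks". The notes to Table 9 in section 11.1 repeat the tolerance: "Imaging evaluation must be done within +/- 7 days of the planned schedule". On cycle length, section 4.1 says "All cycles will be 21-days (3 weeks) in length". On the switch of pembrolizumab schedule it says "After the first 6 months (9 cycles), on C10D1", which equates six months with nine cycles.

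**Event definition (section 13.1.9).** "PFS is defined as the time from the initiation of study treatment to radiographic progression or death".

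**Loss to follow-up (section 14.0).** Patients lost before the six-month evaluation "who did not respond or do not have documented response before their being lost to follow up will be counted as events" if they fall in that group. The count is for the composite primary endpoint, so one rule serves both ORR and 6-month PFS.

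**The concern.** Two features of the rule leave the PFS count open.

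**Timing.** Scans at weeks 9, 18 and 27 put the nearest scan just after six calendar months. The PFS definition and the decision rule, read literally, date progression to when it is seen. A patient whose progression is first seen at day 189 was then progression free at day 183 and is a success. The protocol does not exclude this reading, and it does not adopt the alternative in which the week-27 scan settles the status.

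**Loss.** Making a lost patient's status depend on earlier response is right for ORR, because a documented response has already been achieved. It is wrong for 6-month PFS: a responder lost at month 3 has not been shown to be progression free at month 6, yet the failure rule does not cover that patient.

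At stake is the go/no-go conclusion, and also the interim. With fewer than 6 responses among the first 20 patients, accrual halts until their six-month PFS status is known, so the same undefined status decides whether the second stage opens. In an open-label single-arm trial, the reading should not be left to be settled once the data are known.

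**Working it through.** **Inputs.** PFS rule 14/20 then 23/33, null 53%, alternative 77%; ORR rule 6/20 then 12/33, null 20% (all section 14.0). Scans every 9 weeks ± 7 days (sections 4.1 and 11.1). Cycle length 21 days (section 4.1). Assumptions not in the protocol: constant hazard, and six months = 365.25/2 = 182.6 days = 26.09 weeks.

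**1. Reproducing the plan.** The probability of meeting the PFS rule at true rate p is the sum over x = 14 to 20 of P(X1 = x) × P(X2 ≥ 23 − x), with X1 ~ Bin(20, p) and X2 ~ Bin(13, p).

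- p = 0.53: 0.0281 (stated 0.028); early termination 0.9042 (stated 0.904).
- p = 0.77: 0.8059 (stated 81%).
- Composite with ORR at 20%, taken as independent: 0.0496 (stated bound 0.05).

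The plan's figures reproduce.

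**2. Scan position.** C10D1 comes 9 × 21 = 189 days after C1D1. With ± 7 days the window is days 182-196. Of these 15 days, only one (day 182), or two if day 183 is allowed, lie at or before the six-month mark.

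**3. Calendar reading.** Under the null, the rate still progression free at week 18 is 0.53^(18/26.09) = 0.645. Let c be the share of failures between week 18 and the six-month mark that are still caught in time (deaths, unscheduled or early scans). The rate that is read is 0.645 − c × (0.645 − 0.53).

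| c | Rate read under the null | PFS type I error | Composite type I error |
|---|---|---|---|
| 1 | 0.530 | 0.028 | 0.050 |
| 0.75 | 0.559 | 0.056 | 0.078 |
| 0.5 | 0.588 | 0.102 | 0.126 |
| 0.25 | 0.616 | 0.171 | 0.197 |
| 0 | 0.645 | 0.266 | 0.293 |

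At c = 0 the probability of missing the stage 1 PFS criterion falls from 0.904 to 0.601. This row is an upper bound.

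**4. Nine-cycle reading.** If the week-27 scan decides, the null rate is 0.53^(27/26.09) = 0.518 and the PFS type I error is 0.021. The alternative becomes 0.77^(27/26.09) = 0.763 and power is 0.781.

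**5. Failures that are not counted.** If on average k of 33 true failures are left out of the failure count and scored as successes, the rate read under the null is 0.53 + k/33.

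- k = 1: rate 0.560, PFS type I error 0.058.
- k = 2: rate 0.591, PFS type I error 0.108.
- k = 3: rate 0.621, PFS type I error 0.184.

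**The case against.** The strongest reply is that the protocol points to the week-27 scan. It equates six months with nine cycles in several places, Table 9 places imaging at Cycles 4 and 7 and then from Cycle 10, and section 14.0 speaks of a six-month evaluation and status, not of a cut at a given day. On that reading the rule is slightly conservative. This stands as the more natural intention. But the nine-cycle wording describes dosing, and no sentence ties the endpoint to that scan.

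A reader might go further and infer that the rule in effect reads the week-18 scan, so that the 6-month rate is inflated and the true error is about 0.27. The documents do not support that. It needs the strict calendar reading and no failure at all caught between week 18 and the six-month mark. Deaths in that interval count, and a scan is scheduled at discontinuation. The historical rate that anchors the null is itself scan-based. If the reference trial scanned with a similar lag, part of the difference cancels, and its schedule is not given.

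A reader might also infer a defect from the contrast between treatment continuing "as maintenance therapy until clinical or radiographic progression" (section 10.1) and a PFS definition limited to radiographic progression or death. The primary objective is explicitly radiographic PFS, and the discontinuation scan gives a way to document it. Counting clinical progression or new therapy as events is an endpoint choice, not a correction.

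On loss, it is fair to say that the protocol never calls a lost responder a success, that it expects loss to be uncommon, and that counting lost non-responders as failures works against inflation. Still, the rule as written limits the events to patients without a response.

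Finally, windows and missing-scan rules often belong in the SAP. Here, however, the protocol itself fixes the timepoint, the event definition, the loss rule and the error rates, and these do not fit together.

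**Conclusion.** The point holds as an ambiguity in a co-primary endpoint plus one misdirected loss rule. It does not show that the trial's error rate is inflated. Depending on which scan is taken to decide, the PFS type I error is 0.021 (week-27 scan, power 0.78) or lies above the stated 0.028 on the calendar reading: 0.056 with three quarters of the interval failures caught, 0.10 with half, and no more than 0.27. These figures rest on constant hazard and a 53% null taken as a true six-month rate. The net effect against the historical rate cannot be determined from the protocol.

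The loss rule is a separate fault and does not depend on the scan date. Its effect depends on how many responders are lost and how many of them had in fact failed, which the protocol does not estimate. The margin is thin: one uncounted failure among 33 roughly doubles the PFS type I error.

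**What to change.** In section 14.0, with a matching line in section 13.1:

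- Define 6-month PFS success as alive with no RECIST v1.1 progression up to and including the week-27 scan (C10D1, window days 182-196).
- State that progression first seen at that scan is a failure, whatever its date within the window.
- State that patients lost before that scan are PFS failures regardless of earlier response, unless a later scan shows no progression.
- Keep a separate ORR rule: a patient without a documented response is a non-responder.
- Use the same definition for the stage 1 count of 14 of 20.
- Restate the PFS type I error as about 0.02 and power as about 0.78, with the constant-hazard assumption used to move the 53% and 77% rates from 26.1 to 27 weeks.

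The cost is about one paragraph and no new scans. Stated power falls from 0.81 to 0.78, and slightly further if responders are lost. Thresholds and sample size can stay. Whether clinical progression or new anticancer therapy also counts as a PFS event is optional and can be settled separately.
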